12.3 Treatment Assignment and Blinding

This is an open-label study. The Investigators, other hospital personnel, patients and Sponsor will know the identity of the treatment.

Effort will be made, as appropriate, to maintain continuity of study staff who administer/evaluate various assessments at each site (*i.e.*, PE, morphology/fibrosis grade review, etc.), to facilitate consistency of assessments within a patient.

12.4 Study Populations

- The safety population will include all patients receiving at least one dose of study medication. The safety population will be used to analyze all safety data.
- The mITT population will include all patients receiving at least one dose of study medication and at least one post-baseline result of measure. This will be the primary study population.
- The PK population will include all patients in the safety population who have at least one post dose concentration observation collected.

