6.2 Patient Enrollment

A sufficient number of patients who fulfill the inclusion/exclusion criteria documented in Section 6.1 will be screened to ensure approximately 20 patients are enrolled and treated in this study.

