12.2 Power

This is a single-arm trial with a primary endpoint that is response rate as defined: incidence of patients who achieve a sustained reduction of Hct to <45% for 12 weeks without concomitant phlebotomy by Week 36.

In this study, approximately 20 participants will be enrolled and treated. With 15 observed responders, the estimated clinically meaningful response rate based on response rates for existing agents and its 95% CI are 75% (50.6%, 90.4%). All endpoints will be descriptive, and no formal hypothesis testing will be conducted. [Table 3](#) shows the two-sided 95% CIs for the response rates with 20 participants for different observed response rates based on the method of Clopper and Pearson. ([Clopper and Pearson, 1934](#)). Since this study does not have formal hypotheses to be tested, no power calculations have been conducted.

Table 3: Confidence Intervals for Different Observed Response Rates

Total Sample Size	Observed # of Responders	Observed Response Rate	95% CI (%)
20	13	65	(40.9, 83.7)
	14	70	(45.7, 87.2)
	15	75	(50.6, 90.4)
	16	80	(55.7, 93.4)
	17	85	(61.1, 96.0)
CI, confidence interval.			

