12.5 Primary Analysis

Incidence of patients who achieve a sustained reduction of Hct <45% for 12 weeks without concomitant phlebotomy by Week 36 will be summarized with point estimate and its 95% CI using exact binomial method proposed by Clopper and Pearson ([Clopper and Pearson, 1934](#)). Patients not achieving a response by Week 36 or dropping from the trial but have at least one post-baseline observation will be included in the analysis as a nonresponder.

[figure not shown]
AE verbatim terms will be coded using the Medical Dictionary for Regulatory Activities (MedDRA) and summarized by treatment emergent adverse event (TEAE), Serious TEAE, related TEAE, serious related TEAE, discontinued due to TEAE, TEAE by maximum toxicity grade. Patients will be counted once per unique preferred term and body system. TEAE is defined as any event that occurs on or after the first dose of study drug administration or any preexisting event which worsened in severity after dosing. Frequency and proportion of events will be summarized.

Changes in PEs, vital signs, and laboratory values will be analyzed over time where applicable. Shift tables to worst post-baseline may be produced for specific parameters as detailed in the SAP.

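### The primary response rate omits treated patients with no post-baseline result, and the dropout rule, read literally, recodes patients who had already met the endpoint

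*Combined protocol and SAP*

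**What the plan says.** The primary efficacy endpoint is the proportion of patients who "achieve a sustained reduction of Hct to <45% for 12 weeks without concomitant phlebotomy by Week 36" (Section 12.2; the objective in Section 4.1 is the same). It is to be reported as a point estimate with a Clopper-Pearson 95% interval. There is no hypothesis test, and Section 12.2 states that "no power calculations have been conducted".

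Three statements fix the denominator and the failures:

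- **Target number.** Section 6.2 plans screening so that "approximately 20 patients are enrolled and treated in this study", and Section 12.2 repeats the figure. Table 3 uses n = 20 throughout.
- **Primary population (Section 12.4).** "The mITT population will include all patients receiving at least one dose of study medication and at least one post-baseline result of measure". This mITT set is named as primary. The all-treated set also exists, as the safety population, but is assigned only to safety data.
- **Nonresponders (Section 12.5).** Two groups are joined by ‘or’: patients without a response by Week 36, and patients "dropping from the trial but have at least one post-baseline observation will be included in the analysis as a nonresponder".

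Section 12.6 names no population for the platelet and WBC response proportions. Section 12.1 leaves detailed methods to a separate SAP, whose text is not in the document reviewed.

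**The concern.** There are two issues, and they push the estimate in opposite directions.

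**Denominator.** Sections 12.4 and 12.5 apply the same condition, so a treated patient with no post-baseline result is neither in the mITT set nor imputed as a failure. Such a patient cannot be a responder, so leaving the patient out removes only a failure. In a single-arm trial no comparator loses patients in the same way, and the rate will be read against those of existing agents, as Section 12.2 itself does. Section 12.4 also does not say which measure the required result refers to, so the set is not pinned to hematocrit.

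**Dropout clause.** A patient who leaves before responding already has no response by Week 36 and so falls in the first group. Taken word for word, the second group adds something only if it reaches patients who had responded. It carries no date limit and no exception for them. The endpoint, by contrast, is something achieved by Week 36, and leaving later does not undo it.

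The stake is that two analysts could report different primary rates from the same data. The study is open-label, so the choice should be settled before results are seen.

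**Working it through.** **Inputs.** n = 20 treated (Sections 6.2 and 12.2); 15 responders, the case worked in Section 12.2; two-sided 95% Clopper-Pearson (Sections 12.2 and 12.5). The documents give no dropout rate. The number of treated patients with no post-baseline result (k) and the number of responders recoded after leaving (m) are therefore assumptions, each varied from 0 to 3.

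**Formula.** For x responders of N, the lower limit is the 0.025 quantile of Beta(x, N − x + 1) and the upper limit is the 0.975 quantile of Beta(x + 1, N − x).

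**Step 1: the plan's own figure.** 15/20 = 75% reproduces. The exact interval is (50.9, 91.3); Section 12.2 and Table 3 print (50.6, 90.4). All ten limits in Table 3 match the Wilson interval with continuity correction, not the Clopper-Pearson method the table names. The gaps are at most 1.0 point and do not affect this point. Exact limits are used below.

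**Step 2: exclusions only, x/(20 − k).** Since x/(20 − k) ≥ x/20, the rate can only rise or stay the same.

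| k | 15 responders | 13 responders |
|---|---|---|
| 0 | 15/20 = 75.0% (50.9, 91.3) | 13/20 = 65.0% (40.8, 84.6) |
| 1 | 15/19 = 78.9% (54.4, 93.9) | 13/19 = 68.4% (43.4, 87.4) |
| 2 | 15/18 = 83.3% (58.6, 96.4) | 13/18 = 72.2% (46.5, 90.3) |
| 3 | 15/17 = 88.2% (63.6, 98.5) | 13/17 = 76.5% (50.1, 93.2) |

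**Step 3: recoded responders only, (15 − m)/20.** Each costs 1/20 = 5 points.

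- m = 1: 14/20 = 70.0% (45.7, 88.1)
- m = 2: 13/20 = 65.0% (40.8, 84.6)
- m = 3: 12/20 = 60.0% (36.1, 80.9)

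**Step 4: both, (15 − m)/(20 − k), against 75.0%.**

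- k = 1, m = 1: 14/19 = 73.7% (48.8, 90.9), a change of −1.3 points
- k = 2, m = 1: 14/18 = 77.8% (52.4, 93.6), a change of +2.8 points
- k = 1, m = 2: 13/19 = 68.4% (43.4, 87.4), a change of −6.6 points

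The sign depends on the mix, so the net direction cannot be stated in advance.

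**Step 5: how patients could reach either group.**

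- *Exclusion.* The first scheduled on-treatment hematology is at Week 2 (Section 9.3.2), but it is not the only source. Section 6.6 asks every patient who stops early to return for an EoT visit, or for an ED visit if follow-up is refused. Both include hematology (Sections 9.5.1 and 9.5.2). Only a patient with no post-dose sample at all is lost.
- *Recoding.* A 12-week response can be complete from about Week 12 at the earliest. On the literal reading, exposure runs from there to Week 36, or to the end of the 52-week treatment period because the clause sets no cut-off.

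**The case against.** The strongest reply is that both problems are small or already handled.

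- **Early stoppers are mostly captured.** A reader might infer that anyone who stops before the Week 2 visit leaves the denominator. The documents do not support that: a patient who stops on Day 8 and attends the EoT visit has a post-baseline blood count, enters mITT and is counted as a nonresponder. This stands and limits the first issue to patients with no post-dose sample.
- **The dropout sentence has a benign reading.** A reader might infer that the plan definitely turns responders into nonresponders. Section 12.5 does not say so. The sentence may simply spell out that patients who leave before responding are failures, and the endpoint wording would keep an earlier responder. This stands too: the defect is ambiguous wording that conflicts with the endpoint only if taken literally.
- **The shifts are small beside the uncertainty.** The exact interval for 15/20 is 91.3 − 50.9 = 40.4 points wide, the analysis is descriptive, and Table 3 is illustrative for approximately 20 patients. This is fair as to size. It does not justify leaving a known failure out of the denominator.
- **The SAP may settle it.** It may, but Sections 12.4 and 12.5 already state these rules, and a SAP would have to depart from them.
- **All treated patients would be wrong for the spleen endpoint.** Correct: Section 4.2 restricts that objective to patients with an enlarged spleen at baseline. Nor does the undefined measure in Section 12.4 prove that the denominator changes by endpoint; the text leaves this open.

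**Conclusion.** The point holds in two parts of different strength. On the plain text, Sections 12.4 and 12.5 leave a treated patient with no post-baseline result out of the primary rate. That can only raise the rate or leave it unchanged, and it will probably affect few patients. The second part is conditional: if the dropout clause is applied as written, it recodes patients who met the endpoint and later left, contrary to the definition in Sections 4.1 and 12.2.

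At the planning case of 15/20, one exclusion adds 3.9 points and a second a further 4.4; each recoded responder subtracts 5. These sizes rest on assumed counts. A reader might conclude that the reported rate will be inflated overall, but the documents do not support that, because the two effects oppose each other and neither frequency is given. The issue is modest in size and worth correcting because the correction is simple.

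**What to change.** - **Section 12.4:** for the primary hematocrit response, make all treated patients (the safety population) the primary set, and count those without evaluable post-baseline hematocrit as nonresponders. Do the same for the platelet and WBC response proportions in Section 12.6. Keep the spleen analysis to patients with an enlarged spleen at baseline.
- **Section 12.5:** state that patients who leave before meeting the 12-week criterion are nonresponders, and that patients who met it by Week 36 before leaving remain responders.
- **Sensitivity analysis:** report the response rate in the mITT set as currently defined alongside the primary result.

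The cost is a short rewording of Sections 12.4 and 12.5, carried into Section 12.6 and the SAP. No new patients, visits or data are needed. The downside is that the reported rate may be slightly lower where a treated patient has no post-baseline hematocrit.

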12.5 Primary Analysis

Incidence of patients who achieve a sustained reduction of Hct <45% for 12 weeks without concomitant phlebotomy by Week 36 will be summarized with point estimate and its 95% CI using exact binomial method proposed by Clopper and Pearson ([Clopper and Pearson, 1934](#)). Patients not achieving a response by Week 36 or dropping from the trial but have at least one post-baseline observation will be included in the analysis as a nonresponder.

[figure not shown]
AE verbatim terms will be coded using the Medical Dictionary for Regulatory Activities (MedDRA) and summarized by treatment emergent adverse event (TEAE), Serious TEAE, related TEAE, serious related TEAE, discontinued due to TEAE, TEAE by maximum toxicity grade. Patients will be counted once per unique preferred term and body system. TEAE is defined as any event that occurs on or after the first dose of study drug administration or any preexisting event which worsened in severity after dosing. Frequency and proportion of events will be summarized.

Changes in PEs, vital signs, and laboratory values will be analyzed over time where applicable. Shift tables to worst post-baseline may be produced for specific parameters as detailed in the SAP.

12.6 Secondary Analysis

Incidence of platelet count $\leq 450 \times 10^9/L$ will be analyzed as a proportion. Frequency and percentage of patients achieving at least one result will be counted as a reduction. Similarly, WBC $< 10 \times 10^9/L$ will be analyzed. Durability of hematocrit <45%, platelet count $\leq 450 \times 10^9/L$ and WBC $< 10 \times 10^9/L$ will be analyzed by frequency achieving at least 12, 24, 36, and 52 weeks durable responses.

New thrombotic or hemorrhagic events will be analyzed separately and combined using frequency and percentage. Each patient will be counted once per event. Reduction of spleen volume to Week 36 and Week 52 will be analyzed centrally using percent change from baseline. Change and percent change from baseline in spleen volume will be measured using a continuous measure as well. Frequency and proportion of progression will be analyzed within 36 weeks and 52 weeks. If enough events occur Kaplan-Meier estimates will be graphically displayed.

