4.2 Secondary

- Durability of reduction of hematocrit to <45% without phlebotomy
- Incidence and durability of reduction of platelet count to $\leq 450 \times 10^9/L$
- Incidence and durability of reduction of white blood cell (WBC) count to $<10 \times 10^9/L$
- Incidence of new thrombotic or major hemorrhagic events
- Incidence of achieving a reduction in spleen volume by Week 36 in patients with enlarged spleen at baseline
- Incidence of progression to post-polycythemia vera myelofibrosis (PPV-MF), MDS, or transformation to AML

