6.1.1 Inclusion Criteria

Patients must meet all of the applicable Inclusion Criteria and none of the Exclusion Criteria to be eligible for enrollment in this study:

1. Age ≥ 18 years.
2. History of confirmed diagnosis of Polycythemia Vera *per* World Health Organization (WHO) diagnostic criteria for myeloproliferative neoplasms (Appendix 16.2, [Arber et al., 2016](#)).
3. Bone marrow fibrosis score of Grade 0 or Grade 1, as *per* a slightly modified version (Appendix 16.3, [Arber et al., 2016](#)) of the European Consensus Criteria for Grading Myelofibrosis ([Thiele et al., 2005](#)).
4. Patients that have failed at least one standard cytoreductive therapy to lower hematocrit (failure is the equivalent of resistance or intolerance). A modified version of the European Leukemia Net (ELN) criteria for intolerance or resistance to hydroxyurea is located in Appendix 16.6, [Barosi et al., 2010](#)). Ruxolitinib and interferon refractoriness or intolerance will be left to the discretion of the Investigator.
5. Platelet count $\geq 250 \times 10^9/L$.
6. ANC $\geq 1.5 \times 10^9/L$.
7. Life expectancy > 36 weeks.
8. Able to swallow capsules.

9. Must have discontinued prior cytoreductive therapy for condition under study for 2 weeks (4 weeks for interferon) prior to study drug initiation. Phlebotomy may continue as clinically indicated.
10. Amenable to blood draws, spleen size determination, bone marrow evaluations, and peripheral blood sampling during the study.
11. Participants must agree to use an approved method of contraception from Screening until 30 days after last bomedemstat dose.

Participants Assigned Male Sex at Birth If a participant is capable of producing sperm, the participant agrees to the following during the intervention period and for at least the time needed to eliminate the study intervention after the last dose of study intervention. The length of time required to continue contraception for the study intervention is 30 days:

- Abstains from penile-vaginal intercourse as their preferred and usual lifestyle (abstinent on a long-term and persistent basis) and agrees to remain abstinent

OR

- Uses contraception as detailed below unless confirmed to be azoospermic (vasectomized or secondary to medical cause, documented from the site personnel's review of the participant's medical records, medical examination, or medical history interview) as detailed below:

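### Section 12.6 counts patients who already met the platelet or WBC cut-off at baseline as having a reduction

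*Combined protocol and SAP*

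**What the plan says.** Section 12.6 gives the platelet analysis as "Incidence of platelet count $\leq 450 \times 10^9/L$ will be analyzed as a proportion" and the counting rule as "Frequency and percentage of patients achieving at least one result will be counted as a reduction". White cells follow the same rule: "Similarly, WBC $< 10 \times 10^9/L$ will be analyzed". The section then counts durable responses of at least 12, 24, 36 and 52 weeks at the same cut-offs. Neither part mentions the starting count, and the incidence rule does not say that the qualifying value must be post-baseline.

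Section 4.2 words the objective as a change: "Incidence and durability of reduction of platelet count to" 450 ×10⁹/L, with a parallel objective for WBC. The spleen objective in the same list is limited to patients whose spleen is enlarged at baseline. The platelet and WBC objectives carry no such limit.

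Section 6.1.1 requires platelets of at least 250 ×10⁹/L and ANC of at least 1.5 ×10⁹/L. Neither 6.1.1 nor 6.1.2 restricts total WBC. The prior-failure criterion is framed around hematocrit ("Patients that have failed at least one standard cytoreductive therapy to lower hematocrit"). Under Appendix 16.6, hydroxyurea resistance can be met through phlebotomy need alone.

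Section 12.4 makes the mITT set primary, with no condition on baseline counts. Section 12.1 defines baseline, but 12.6 does not use it for these two incidence endpoints.

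**The concern.** The label and the rule measure different things. A patient with platelets of 400 on Day 1 and 430 at Week 2 has had a rise, yet meets the rule for a reduction. A patient stable at 300 throughout would also count in the durability tiers. The reported percentage therefore mixes drug effect with the baseline case mix of about 20 patients. A single-arm trial has no comparator group to show how much of the rate comes from patients who needed no change. The error runs in one direction: it can raise the rate but never lower it.

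**Working it through.** **Step 1. Can patients enter already meeting the cut-off?** Yes. Platelets from 250 to 450 satisfy both the entry criterion (6.1.1) and the endpoint (12.6). For WBC, entry sets only a neutrophil floor, so a total count below 10 is allowed. Section 4 describes thrombocytosis and leukocytosis as frequent in PV, not universal.

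**Step 2. How does the rule score them?** Such a patient fails only if every post-baseline value lies above a cut-off that the patient was already under, while taking a drug expected to lower these counts. Success is near-certain. If a baseline value were allowed to count, which 12.6 does not exclude, success would be automatic.

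**Step 3. Size.** The plan states no figure for these endpoints, so there is nothing to reproduce. Inputs: n = 20 (Section 12.2); m = patients already meeting the cut-off at baseline (not in the documents, so a range is assumed); c = patients among the other 20 − m who truly convert. All m are taken as successes.

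- Rate as written: (m + c)/20
- Rate among patients who can show a reduction: r = c/(20 − m)
- Excess: (m + r(20 − m))/20 − r = m(1 − r)/20, which is never negative

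| m | c | As written (95% CI) | Restricted (95% CI) |
|---|---|---|---|
| 2 | 0 of 18 | 2/20 = 10% | 0% |
| 4 | 0 of 16 | 4/20 = 20% | 0% |
| 8 | 0 of 12 | 8/20 = 40% | 0% |
| 4 | 8 of 16 | 12/20 = 60% (36.1–80.9) | 8/16 = 50% (24.7–75.3) |
| 8 | 6 of 12 | 14/20 = 70% (45.7–88.1) | 6/12 = 50% (21.1–78.9) |

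Intervals are Clopper-Pearson and are shown for the half-converting rows. The excess formula gives 4 × 0.5/20 = 10 points and 8 × 0.5/20 = 20 points, as in the table.

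**Step 4. What might m be?** The only relevant platelet figure is a mean of 720 ×10⁹/L at PV diagnosis (Section 3.7.1), with no SD. Assume an SD of 150 to 400 and a normal or lognormal shape, truncated below at 250. The share between 250 and 450 is [F(450) − F(250)]/[1 − F(250)], which runs from 1.5% to 23.0%. Times 20, that is 0.3 to 4.6 patients, or about 0 to 5. This is a rough guide only: the mean is at diagnosis, whereas trial patients have since had cytoreductive therapy and a washout. On it, m = 8 is high for platelets. No WBC distribution is given, so m for WBC cannot be bounded.

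**The case against.** Several points on the other side stand.

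- **These are descriptive secondary endpoints.** Section 12.2 plans no hypothesis tests. No error rate or sample size depends on these counts. A reader might infer that the trial's main efficacy result is biased; it is not, because the primary endpoint in Section 12.5 is sustained hematocrit control without phlebotomy.
- **The durability tiers deal with isolated values.** A reader might infer that repeated testing lets chance dips dominate the results. The documents give no per-visit probability of a dip. Serial counts in one patient are correlated, and dosing responds to the platelet count, so a calculation that treats visits as independent would mislead. Persistence is already reported at 12 to 52 weeks. What the tiers do not supply is a starting condition.
- **Very low platelet counts also qualify.** A reader might call this toxicity scored as efficacy. A fall from above 450 to a very low count is still a reduction, and Section 3.7.1 treats the platelet count as a marker of both safety and efficacy. Excluding such values is a choice about the question asked, not the correction of an error.
- **The inflation may be small for platelets.** Section 3.5.3 reports that 35 of 36 ET patients treated for more than 36 weeks reached platelets ≤400 ×10⁹/L. At that conversion rate, m = 4 adds 4 × (1/36)/20 = 0.6 points. But that is another disease and a subset still on treatment, and no comparable figure is given for WBC.
- **Appendix 16.5 defines count remission by absolute levels, without a baseline condition.** Those criteria describe a remission state within a composite. Section 4.2 names a reduction.
- **Section 12.1 leaves detail to a separate SAP.** That SAP text is not in the document reviewed and might add a restriction. Section 12.6 nevertheless already states an operative rule, which the SAP would have to override.

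**Conclusion.** The point holds and should be fixed, but it does not threaten the trial's main conclusion. As written, the platelet and WBC incidence rates and the matching durability counts include patients who had nothing to reduce. The excess is m(1 − r)/20. It is zero if nobody starts at or below the cut-off or if everyone else converts. It is 10 points at m = 4 and 20 points at m = 8 when half of the rest convert, and 20 and 40 points when none do.

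These sizes rest on an assumed m, on 20 analysed patients, and on every already-low patient being scored a success. The direction of the bias rests only on the wording of 12.6 and the entry criteria.

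**What to change.** In Section 12.6 and the SAP:

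- For platelet incidence and for platelet durability at 12, 24, 36 and 52 weeks, use as denominator the patients with baseline platelets >450 ×10⁹/L.
- For WBC, do the same with patients whose baseline WBC is ≥10 ×10⁹/L.
- Take baseline as defined in Section 12.1, and state that only post-baseline values count.
- Report patients already meeting the cut-off in a separate line as maintained or not maintained, with their number.

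No extra confirmation rule is needed, because the durability tiers already report persistence.

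The cost is wording only; no new data are collected. Denominators shrink, intervals widen (for m = 8, 6/12 has 21.1–78.9% against 45.7–88.1% for 14/20) and the rates become less favourable. One consequence should be stated: the first scheduled post-baseline count is at Week 2, so at nominal timing a run observed to Week 52 covers at most 52 − 2 = 50 weeks. The 52-week tier could then be met only by patients followed longer in this study. The change should be settled before analysis, because in an open-label trial a later choice would be made with the results in view.
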